8.3.11 LONG-TERM SAFETY FOLLOW-UP

For long-term safety follow-up of subjects there will be a Week 24, Week 36, and Week 60 safety follow-up visit. The same study procedures will be conducted at all three visits, as outlined in Table 1 (Schedule of Activities). The Month 3 Safety Follow-up Visit (Week 24 Visit) will take place 12 weeks after the Week 12 or ET visit with a two week visit window. The Month 6 Safety Follow-Up Visit (Week 36 visit) will take place 24 weeks after the Week 12 or ET visit with a two week visit window. The Month 12 Safety Follow-up Visit (Week 60) will take place a year from the Week 12 or ET visit.

8.4 UNANTICIPATED PROBLEMS

8.4.1 DEFINITION OF UNANTICIPATED PROBLEMS (UP)

The Office for Human Research Protections (OHRP) considers unanticipated problems involving risks to participants or others to include, in general, any incident, experience, or outcome that meets **all** of the following criteria:

- Unexpected in terms of nature, severity, or frequency given (a) the research procedures that are described in the protocol-related documents, such as the Institutional Review Board (IRB)-approved research protocol and informed consent document; and (b) the characteristics of the participant population being studied;
- Related or possibly related to participation in the research (“possibly related” means there is a reasonable possibility that the incident, experience, or outcome may have been caused by the procedures involved in the research); and
- Suggests that the research places participants or others at a greater risk of harm (including physical, psychological, economic, or social harm) than was previously known or recognized.

8.4.2 UNANTICIPATED PROBLEM REPORTING

The investigator will report unanticipated problems (UPs) to the reviewing Institutional Review Board (IRB) and to the Data Coordinating Center (DCC)/lead principal investigator (██████████). The UP report will include the following information:

- Protocol identifying information: protocol title and number, PI’s name, and the IRB project number;
- A detailed description of the event, incident, experience, or outcome;
- An explanation of the basis for determining that the event, incident, experience, or outcome represents an UP;
- A description of any changes to the protocol or other corrective actions that have been taken or are proposed in response to the UP.

To satisfy the requirement for prompt reporting, UPs will be reported using the following timeline:

- UPs that are serious adverse events (SAEs) will be reported to the IRB and to the DCC/study sponsor within 7 calendar days of the investigator becoming aware of the event.
- Any other UP will be reported to the IRB and to the DCC/study sponsor within 7 calendar days of the investigator becoming aware of the problem.

- All UPs should be reported to appropriate institutional officials (as required by an institution's written reporting procedures), the supporting agency head (or designee), and the Office for Human Research Protections (OHRP) within 30 days of the IRB's receipt of the report of the problem from the investigator.

8.4.3 REPORTING UNANTICIPATED PROBLEMS TO PARTICIPANTS

N/A

9 STATISTICAL CONSIDERATIONS

9.1 STATISTICAL HYPOTHESES

The primary end-point of the study and on which the statistical power is based is the percent change in ALT from Baseline to Week 12.

The hypothesis being tested is that treatment with gemcabene for twelve weeks will result in a clinically meaningful reduction in ALT, in pediatric NAFLD participants.

9.2 SAMPLE SIZE DETERMINATION

The sample size for this study is 36 completed participants. A percent change from baseline of approximately 20% is considered to be clinically meaningful. Assuming a two-sided test at the 5% significance level, 36 completed participants will provide 81% power to detect a percent change from baseline of 20% (effect size = 0.5), if the standard deviation is 40%. Additionally, assuming a drop-out rate of 10%, a total of 40 participants is needed for enrollment into the study to ensure an adequate number of subjects complete the trial. Power was calculated using a two-sided Wilcoxon test with a 0.05 significance level using PASS v. 14.0.8 (Kaysville, UT).

9.3 POPULATIONS FOR ANALYSES

- Intention-to-Treat (ITT) Analysis Set: all enrolled participants. All efficacy summaries and analyses will be performed using the ITT.
- Modified Intention-to-Treat Analysis (mITT) Set: all enrolled participants who took at least one dose of study intervention and have liver enzymes performed at Baseline and Week 12. Confirmatory efficacy analyses will be performed using the mITT.
- Safety Analysis Set (SAS): all enrolled participants who took at least one dose of study intervention. All safety summaries will be performed using the SAS.
- Per-Protocol Analysis Set (PPAS): the subset of the participants in the full analysis (ITT) set who complied with the protocol sufficiently (e.g., took at least 80% of study intervention for 80% of the days within the 12-week period) and did not have any major protocol deviations. Confirmatory efficacy and safety analyses will be performed using the PPAS.

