1.2 SCHEMA

1.3 SCHEDULE OF ACTIVITIES (SOA)

Table 1. Schedule of Activities

| | Screening (-6 weeks) | Baseline (Day 1 +/- 2 days) | Week 2 (Day 15+/- 7 days) | Week 6 (Day 43+/- 10 days) | Week 12 (Day 85 +/- 10 days) | Week 16 Follow- up (phone call) Day 113 +/- 10 days | Early Termination Visit | Week 28 Long-Term Follow-up (Month 3) +/- 2 weeks | Week 36 Long-Term Follow-up (Month 6) +/- 2 weeks | Week 60 Long-Term Follow-up (Month 12) +/- 2 weeks |
|--|-------------------------|--------------------------------------|------------------------------------|--|---|---|-------------------------------|---|---|--|
| Informed Consent and HIPAA Authorization | X | | | | | | | | | |
| Review Inclusion/Exclusion Criteria | X | X | | | | | | | | |
| Demographics & Medical History | X | | | | | | | | | |
| Physical Exam | | X | | | X | | X | X | X | X |
| Vital Signs ^A | X | X | X | X | X | | X | X | X | X |
| Standardized lifestyle counseling | | X | | | | | | | | |
| Height, weight, (calculated BMI) waist and hip measurements ^C | X | X | X | X | X | | X | X | X | X |
| Alcohol Use Disorders Identification Test (AUDIT) | X | | | | | | | | | |
| Dietary Assessment (Food Frequency Questionnaire) | | X | | | X | | X | | | |
| MRI | | X | | | X | | X | X | X | X |
| ECG | | X | X | | | | | | | |
| PROMIS Questionnaires (fatigue, depression, anxiety) | | X | | | X | | X | | | |
| Beverage Questionnaire | | X | | | X | | X | | | |
| Tanner Staging (self-administered) | X | | | | | | | | | |
| Physical Activity Assessment (Block) | | X | | | X | | X | | | |
| Local Urine Pregnancy Test (WOCBP) | | X | X | X | X | | X | X | X | X |
| Urinalysis (UA) | X | X | X | X | X | | X | X | X | X |
| Blood Draw ^B | X | X | X | X | X | | X | X | X | X |

| | | | | | | | | | | |
|----------------------------------|---|---|---|---|---|---|---|---|---|---|
| De novo lipogenesis (substudy) | | X | | | X | | | | | |
| Postprandial lipid (substudy) | | X | | | X | | | | | |
| Instructions for Drug Compliance | | X | X | X | | | | | | |
| Drug Dispense | | X | | X | | | | | | |
| Identify clinical follow-up plan | | | | | X | | X | | | |
| Adverse Events Review | | X | X | X | X | X | X | X | X | X |
| Concomitant Medication Review | X | X | X | X | X | X | X | X | X | X |
| Assess Drug Accountability | | | X | X | X | | X | | | |

A – Vital signs to include: temperature, pulse, respirations, and seated blood pressure

B – See details below in Table 2. Blood Draw Schedule

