6.1.2 DOSING AND ADMINISTRATION

The dose is 300 mg orally once a day.

The first dose of study drug will be administered at the research site on Study Day 1. On days with a scheduled office visit with blood sample collection, subject will remain fasted and should not take gemcabene until after the blood samples are collected at the site. On all other days, the subject will self-dose: taking study drug at the same time in the morning with a full glass (8 ounces) of water either with or without food. If a subject misses a dose prior to 6:00 PM, then the subject should take their dose. However, if past 6:00 PM, the subject should not dose and then count the dose as a “missed dose.” The subject will resume normal dosing the next day (i.e., do not take two doses the following day).

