9.4.4 SAFETY ANALYSES

Each AE will be counted once only for a given participant in each summary table, and will be presented based on severity, frequency, and relationship of AEs to study intervention by System Organ Class (SOC) and preferred term groupings. For each AE, the severity, relationship, expectedness, outcome, and duration will be presented in a table. Adverse events leading to premature discontinuation from the study intervention and serious treatment-emergent AEs will be presented either in a table or a listing. AEs will be tabulated and described using counts and percentages with associated 95% confidence intervals.

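### The per-protocol safety analysis called confirmatory leaves out, under the stated 80% adherence example, children permanently taken off drug at Week 2 or Week 6, so it cannot confirm the Safety Set result

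*Combined protocol and SAP*

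**What the plan says.** Section 9.3 defines the Safety Analysis Set as every enrolled child dosed at least once and states: "All safety summaries will be performed using the SAS". It then defines the Per-Protocol Analysis Set as the part of the ITT set that complied well enough. Compliance is illustrated, after an 'e.g.', by children who "took at least 80% of study intervention for 80% of the days within the 12-week period". Members must also be children who "did not have any major protocol deviations"; what counts as major is not defined. The entry ends: "Confirmatory efficacy and safety analyses will be performed using the PPAS".

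Section 9.4.4 describes adverse-event tables with counts, percentages and 95% confidence intervals, and adds: "Adverse events leading to premature discontinuation from the study intervention and serious treatment-emergent AEs will be presented either in a table or a listing". It names no analysis set.

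**The concern.** Drug actually taken is a post-baseline variable that intolerance reduces. Sections 8.2, 8.3.10 and 10.1.2 contain rules under which gemcabene is interrupted or stopped for liver enzymes, creatinine or graded adverse events. A child stopped under one of these rules loses doses because of the event, and the lost doses then remove the child from the set in which safety is to be confirmed. The timing matters: Section 2.3.1 reports that creatinine and BUN rises in earlier studies appeared in the first 2 to 4 weeks, so a stop for that reason would tend to come early.

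Safety is part of the primary objective, and tolerance is a listed secondary endpoint (Section 1.1). Section 2.2 treats tolerability in children as a critical question and presents the trial as support for later phases. A per-protocol table with no discontinuations for toxicity, labelled confirmatory, could be read as corroborating the Safety Set result when it has no means of contradicting it on that item.

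**Working it through.** The plan gives no figure for this point. The only planned numbers used below are 36 completers and 40 enrolled (9.2), which agree with each other: 36 / (1 - 0.10) = 40.

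**1. Inputs.**
- Section 6.1.2: "The dose is 300 mg orally once a day", so 12 weeks is 84 doses.
- Section 6.1.2: on visit days a child "should not take gemcabene until after the blood samples are collected at the site". A permanent stop at a visit on Day d therefore leaves d - 1 doses taken, or d if the visit-day dose is still given.
- Table 1 windows: "Week 2 (Day 15+/- 7 days"), so Day 22 at the latest; Week 6 is Day 43 +/- 10, so Day 53 at the latest; Week 12 is Day 85 +/- 10, so Day 75 at the earliest.

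**2. Thresholds.** Read as 80% of doses: 0.80 x 84 = 67.2, so 68 doses are needed. Read most loosely, as 80% of 80%: 0.64 x 84 = 53.76, so 54 doses are needed.

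**3. Doses at a permanent stop on the visit day.**

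| Stop at | Day used | Doses | Share of 84 | 68 doses met? | 54 doses met? |
|---|---|---|---|---|---|
| Week 2 | 22 (latest) | 21-22 | 25.0-26.2% | no | no |
| Week 6 | 53 (latest) | 52-53 | 61.9-63.1% | no | no |
| Week 12 | 75 (earliest) | 74-75 | 88.1-89.3% | yes | yes |

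**4. Stop after a repeat test.** Section 8.3.10 calls for repeat testing within 48-72 hours, and 10.1.2 for a repeat within a week. After a Day 53 draw, a stop on Day 56 gives 55/84 = 65%, and on Day 60 gives 59/84 = 70%. These children still fail the 80% reading but pass the 64% reading. So exclusion is firm under the 80% reading; under the loosest reading it holds only for stops on the visit day.

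**5. Who stays in.** Up to 84 - 68 = 16 missed doses are compatible with membership. The set keeps children with events who went on dosing, those with interruptions totalling no more than 16 days, those stopped between visits after 68 doses, and otherwise adherent children whose abnormality first appears at Week 12.

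**6. Which rules can act at these visits.** Table 2 schedules the chemistry panel (ALT, AST, creatinine) at Weeks 2 and 6. The blood count is scheduled only at Screening, Week 12, early termination and long-term follow-up, so the hemoglobin rules are not triggered by the scheduled Week 2 or Week 6 draws.

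**7. Illustration (assumed counts, exact 95% intervals).** Children stopped for toxicity at Week 2 or Week 6, with nobody else excluded:

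| Stops | Safety Set | Per-protocol set |
|---|---|---|
| 1 | 1/40 = 2.5% (0.1 to 13.2%) | 0/39 (0 to 9.0%) |
| 2 | 2/40 = 5.0% (0.6 to 16.9%) | 0/38 (0 to 9.3%) |
| 4 | 4/40 = 10.0% (2.8 to 23.7%) | 0/36 (0 to 9.7%) |

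Four would use the whole 10% dropout allowance. The adult figure in Section 2.2 is 17 drug-related discontinuations among 1272 people: 17/1272 x 40 = 0.5 children. With the 901 exposed as denominator, 17/901 x 40 = 0.75.

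**8. Overall adverse-event rate (assumed counts).** Suppose 18 of 40 children (45%) have an event and four are excluded. If all four had events, the per-protocol rate is 14/36 = 39%. If none did, it is 18/36 = 50%. The direction is not fixed.

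**The case against.** The strongest reply is that no planned safety table loses an early stopper. Section 9.3 puts all safety summaries on the Safety Analysis Set, and the 9.4.4 tables are such summaries. Under 10.1.2 the DSMB reviews all adverse events. The per-protocol output is an addition. This stands.

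The word *confirmatory* is also used loosely. Section 9.3 applies it to the mITT efficacy analyses as well, while 9.4.2 makes the ITT analysis primary and treats mITT and per-protocol as similar repeats. In practice it seems to mean supportive. Section 4.1 says in general terms that the drug will be safe, but 9.1 and 9.4.4 set up no safety hypothesis to confirm. This also stands, and it makes the defect partly one of labelling. It does not make the analysis informative: a set that drops early stoppers cannot support a finding about them.

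The 80% rule is only an example, and a child stopped under a protocol rule could be argued to have complied sufficiently. That makes exclusion likely rather than certain, and it leaves membership to judgement in an open-label trial.

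Three stronger readings are tempting, and the documents do not support them:
- *The safety result rests only on children who tolerated the drug.* Step 5 shows otherwise.
- *Adverse-event and laboratory-abnormality rates are understated by construction.* Only the count of early stops for toxicity is sure to fall; step 8 shows the overall rate can move either way.
- *Every stopping rule acts through the Week 2 and Week 6 laboratory draws.* The hemoglobin rules do not (step 6), and the graded adverse-event rule is not tied to a laboratory visit.

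**Conclusion.** The point holds as a defect in one additional analysis. As written, 9.3 calls confirmatory a safety analysis in a set that, under its 80% example, excludes any child permanently stopped at Week 2 (at most 26% of doses) or Week 6 (at most 63%). For toxicity stops at those visits the per-protocol count is zero whatever the drug does, so agreement with the Safety Set carries no information on that item.

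This assumes that the 80% example is applied as the rule, that adherence is measured against the 84-day course, and that the stop is permanent. The main safety result is not compromised. The likely number of children affected is unknown; scaling the adult figure gives fewer than one in 40, although adults and shorter exposures may not carry over to this population. That a favourable per-protocol table would mislead a later-phase decision is possible, but the documents do not show it.

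**What to change.** 1. In 9.3, delete the words *and safety* from the last sentence of the per-protocol entry. If the sponsor wants to keep the analysis, call it supplementary, state that it will not be used for safety conclusions, and replace the 'e.g.' with a fixed adherence rule so that membership is not a matter of judgement.
2. In 9.4.4, name the Safety Analysis Set as the set for all safety tables and conclusions. This also removes the tension within 9.3 between the two safety assignments.

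The cost is one phrase deleted and one sentence added, with one analysis fewer to run if the deletion is chosen. No patients, visits, data or clinical rules change.

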9.4 STATISTICAL ANALYSES

9.4.1 GENERAL APPROACH

Statistical significance will be assessed at the 0.05 level, unless otherwise noted.

Descriptive statistics will be calculated for all variables of interest and include means and standard deviations or medians and ranges (for continuous measures) or counts and percentages (for categorical measures), as appropriate. Continuous data will be assessed for normality using histograms and normal probability plots and statistically tested using the Anderson-Darling test and/or the Shapiro Wilk test for normality. Non-normal data will be presented using medians accompanied by 25th and 75th. All analyses will be conducted using SAS v. 9.4 (Cary, NC) or CRAN R v. 3.3 (Vienna, Austria).

9.4.2 ANALYSIS OF THE PRIMARY EFFICACY ENDPOINT(S)

For the primary efficacy endpoint, we will use the ITT population. The entire population, regardless of whether or not they took the study medication, will be used in the analysis.

- **Percent change in ALT**
Changes in our primary continuous outcome measures (ALT) from Baseline to the primary endpoint (Week 12), will be examined as percentage change.
$$\left(\left(\frac{\text{postbaseline value} - \text{baseline value}}{\text{baseline value}} \right) \times 100 \right)$$
. Statistically, percent change from Baseline to Week 12 will be tested against the null hypothesis of no change (i.e., percent change = 0) using a one-sample two-sided t-test or a Wilcoxon signed-rank test, in the event that the percent change is non-normally distributed. Output from the t-test will include the mean percent change, its 95% confidence interval and the p-value. If the data are non-normally distributed, the median percent change value and the 25th and 75th percentiles will be presented, along with the p-value from the Wilcoxon signed-rank test.
- Patients with no week 12 measurements will be excluded from the primary efficacy analysis (only observed case data will be used). In a sensitivity analysis, for subjects with missing week 12 data, we will carry forward their week 6 measurements and re-assess the primary outcomes. Similar analyses will be used to examine the mITT and the PPAS datasets.

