7 STUDY INTERVENTION DISCONTINUATION AND PARTICIPANT DISCONTINUATION/WITHDRAWAL

7.1 DISCONTINUATION OF STUDY INTERVENTION

Discontinuation from gemcabene does not mean discontinuation from the study, and remaining study procedures should be completed as indicated by the study protocol. If a clinically significant finding is identified (including, but not limited to changes from baseline) after enrollment, the investigator or qualified designee will determine if any change in participant management is needed. Any new clinically relevant finding will be reported as an adverse event (AE).

The data to be collected at the time of study intervention discontinuation (Early Termination Visit) will include the following:

- Blood tests
- MRI
- Vital signs, physical measurements, and a physical examination
- Questionnaires (Food Frequency Questionnaire, PROMIS Questionnaires, Beverage Questionnaire, Physical Activity Assessment)
- Urine collection and pregnancy test (in WOCBP)
- Adverse event and concomitant medication review

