7.3 LOST TO FOLLOW-UP

A participant will be considered lost to follow-up if he or she fails to return for 2 scheduled visits and is unable to be contacted by the study site staff.

The following actions must be taken if a participant fails to return to the clinic for a required study visit:

- The site will attempt to contact the participant and reschedule the missed visit and counsel the participant on the importance of maintaining the assigned visit schedule and ascertain if the participant wishes to and/or should continue in the study.
- Before a participant is deemed lost to follow-up, the investigator or designee will make every effort to regain contact with the participant (where possible, 3 telephone calls and, if necessary, a certified letter to the participant's last known mailing address or local equivalent methods). These contact attempts should be documented in the participant's medical record or study file.
- Should the participant continue to be unreachable, he or she will be considered to have withdrawn from the study with a primary reason of lost to follow-up.

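### The primary ALT analysis is labelled ITT but is observed-case, its one missing-data check cannot reach children who leave before Week 6, and its Wilcoxon branch reports no confidence interval

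*Combined protocol and SAP*

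**What the plan says.** **Population.** Section 9.3 defines ITT as all enrolled children, and mITT as those with at least one dose who also "have liver enzymes performed at Baseline and Week 12". Section 9.4.2 assigns the primary analysis to ITT: "The entire population, regardless of whether or not they took the study medication, will be used in the analysis". It then adds: "Patients with no week 12 measurements will be excluded from the primary efficacy analysis (only observed case data will be used". For children without Week 12 data, the one sensitivity analysis is that "we will carry forward their week 6 measurements and re-assess the primary outcomes".

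**Available ALT.** Table 2 schedules the local metabolic panel, which contains ALT, at Week 2 and at the Early Termination (ET) visit. Central ALT is scheduled at Baseline, Week 6, Week 12 and ET. Section 7.1 introduces the ET list with "The data to be collected at the time of study intervention discontinuation (Early Termination Visit) will include the following", and blood tests head that list. Section 8.1 uses central values for outcomes and falls back on the local value if the central one is missing. Section 9.4.2 gives the ET and Week 2 values no role.

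**Choice of test.** Section 9.4.1 assesses normality with histograms, probability plots, and the Anderson-Darling test, the Shapiro-Wilk test or both, under a general 0.05 level. Section 9.4.2 then gives either a one-sample t-test with mean, 95% CI and p-value, or a Wilcoxon signed-rank test with median, quartiles and p-value. Section 9.2 bases power on the Wilcoxon test.

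**The concern.** The two statements about the primary population cannot both hold, and a reader of the eventual report would take ITT at face value. The mITT run looks like a second view of the data but is close to a repeat of the first. A child who leaves before Week 6 enters no analysis of Week 12 ALT, even though one or two post-baseline ALT values may exist. There is no control arm in which similar losses might offset this.

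Separately, a data-dependent step with no order of precedence decides what the headline number estimates and whether it carries an interval. Section 2.2 says the trial is meant to support later-phase trials. For that purpose the estimate and its precision matter more than the p-value.

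**Working it through.** **1. The plan's own figures.** Inputs from Section 9.2: 36 completers, change 20%, SD 40% (effect size 0.5), two-sided 5%, Wilcoxon, 10% dropout.
- Wilcoxon power, from the noncentral t with effective n = 36 × 3/π = 34.4: 0.812. Simulation gives 0.815. The stated 81% reproduces.
- One-sample t-test at n=36: 0.831.
- Enrolment: 36/0.9 = 40, so about 4 children without Week 12 data are expected.

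**2. The analysis sets side by side.**
- Primary, as actually run: enrolled, with Baseline and Week 12 ALT.
- mITT: the same, plus at least one dose. Section 6.1.2 says "The first dose of study drug will be administered at the research site on Study Day 1", so the two differ only by never-dosed children who have both values.
- Carry-forward: adds children with a Week 6 but no Week 12 value. If k of the 4 leave before Week 6, it covers 40 − k children. At k = 4 it returns the same 36 children and the same result.

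**3. Size of the dropout effect.** The 95% CI half-width at n=36 is 2.030 × 40/√36 = 13.5 points.

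Simulation with true mean −20%, SD 40%, N=40 and 10% dropout. Assumed, not in the documents: Week 6 to Week 12 correlation 0.7; dropout odds multiplied by 1.5 / 2 / 3 per SD of ALT change; 75% of the final effect reached by Week 6 and 35% by Week 2; ET at Day 64 for late leavers and Day 29 for early leavers. Mean percent change:

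| Who leaves | Completers | Planned carry-forward | Last available ALT, incl. ET |
|---|---|---|---|
| All after Week 6 | −21.1 / −21.9 / −22.7 | −19.0 / −18.8 / −18.4 | −19.5 / −19.4 / −19.2 |
| All before Week 6 | −20.8 / −21.5 / −22.2 | identical to completers | −18.7 / −18.4 / −18.0 |
| Half and half | −21.0 / −21.7 / −22.5 | −20.0 / −20.2 / −20.4 | −19.2 / −18.9 / −18.7 |

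- The completer bias is about 1 to 3 points. It reaches 3.4 with correlation 0.85 and odds ×3, all leaving after Week 6.
- If dropout is unrelated to ALT, completers average −19.9 to −20.1, so there is no bias.
- With no true change, completers show a significant decrease in 3.6 / 4.5 / 5.9% of trials (all leaving late) and 3.4 / 4.4 / 4.9% (all leaving early), against a nominal 2.5%.

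A fixed-value illustration: 36 observed at mean −20%, SD 40%, and 4 missing children assigned a value v. The mean is (36 × −20 + 4v)/40.
- v = 0: −18.0 (95% CI −30.3 to −5.7).
- v = +20: −16.0 (p = 0.015).
- v = +40: −14.0 (p = 0.042).
- With an observed mean of −15% and v = +20: −11.5 (p = 0.07).

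**4. The normality switch at n=36** (20,000 runs). The log-normal case is assumed: ratio mean 0.8 and SD 0.4, so log-variance = ln(1 + 0.25) and log-SD = 0.472, with median change 0.8/√1.25 − 1 = −28%.

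| | Normal | Log-normal |
|---|---|---|
| Shapiro-Wilk sends to no-CI branch | 5.0% | 76.3% |
| Anderson-Darling does so | 5.1% | 68.9% |
| The two tests disagree | 3.3% | 9.0% |
| Power, t-test | 83% | 79% |
| Power, Wilcoxon | 81% | 91% |

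In the log-normal case the mean is −20%, the Hodges-Lehmann target about −24% and the median −28%, so the branch changes the reported effect. Rejection rates at log-SD 0.3 / 0.4 / 0.5:
- True mean 0: two-stage rule 7.6 / 9.6 / 12.8%; t-test alone 5.6 / 5.8 / 6.5%.
- True median 0: two-stage rule 9.1 / 10.7 / 11.1%; t-test alone 10.7 / 15.0 / 19.4%.

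Neither approach is the safer one until the target is named.

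**The case against.** The strongest reply is that little of this changes a number. The observed-case rule is disclosed in the same section as the ITT label, and the trial is sized on 36 completers, so power and analysis agree. That stands: the label is wrong, but the sample size is not.

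Section 7.1 also limits losses ("Discontinuation from gemcabene does not mean discontinuation from the study, and remaining study procedures should be completed as indicated by the study protocol"), and Section 8.1 fills a missing central value from the local laboratory. Both stand. Neither helps a child who misses the visit, and Section 7.3 foresees children lost because the child "fails to return for 2 scheduled visits and is unable to be contacted by the study site staff", some of whom may have no ET draw. For children who leave after Week 6, the planned carry-forward does expose the bias. ALT-related dropout and its strength are assumptions. Section 7.2 may also allow some very early leavers to be replaced: it lets never-dosed children be replaced, rules this out after more than 4 weeks of drug, and is silent in between.

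A last-available analysis is not clearly better. If all leave before Week 6, it misses −20 by 1.3 / 1.6 / 2.0 points against 0.8 / 1.5 / 2.2 for completers. In the half-and-half case the planned carry-forward is closer. This stands and determines how the added analysis should be described.

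A reader might infer that the normality check is undefined. It is not: Section 9.4.1 names plots, tests and a default level, and only precedence is missing. A reader might also infer that the t-test must replace the switch. The documents do not support that either: power rests on the Wilcoxon test, and under skew the t-test falls to about 79%, below the planned 81%.

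**Conclusion.** The point holds in a limited form. The contradiction over the population is certain from the text, and correcting it changes no result. It is equally certain that the one missing-data check adds nobody without a Week 6 value, and that the Wilcoxon branch lists no CI.

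The size of any dropout bias, about 1 to 3 points beside a 13.5-point half-width, rests wholly on assumed ALT-related dropout. In the fixed-value range tried, four exclusions do not overturn a result at the planned −20%; they can when the observed effect is smaller, for example −15%. The 5% to 76% range for the no-CI branch depends on the distribution of percent change, which the documents do not give.

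A reader might take the 7.6 to 12.8% rejection rates as plain false-positive inflation. They are not: in those scenarios the medians are −4 / −8 / −12%, so the Wilcoxon test is detecting a real shift in a different quantity. What they show is that the target has to be named. The two changes of most value are a CI in either branch and one analysis that includes early leavers.

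**What to change.** 1. In Section 9.4.2, call the primary analysis observed-case (enrolled children with Baseline and Week 12 ALT) and delete the sentence promising the whole population. Report how many enrolled children are excluded and whether they left before or after Week 6.
2. Add one supportive sensitivity analysis in all enrolled children with any post-baseline ALT, using the last value up to Day 95 (the end of the Week 12 window, 85 + 10). Include ET values and the Week 2 local ALT, and pair a local value with the local Baseline. A true Week 12 draw takes precedence over an ET draw. Present it as a check that includes early leavers, not as a less biased estimate.
3. Report a 95% CI whichever test is used: the mean with its t-interval, and the Hodges-Lehmann estimate with its CI beside the median and quartiles.
4. Name in advance one primary test and its target (mean or pseudomedian), or one governing normality rule. The choice between t-test and Wilcoxon is the sponsor's, on the power trade-off shown above.

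The cost is wording in Sections 9.4.1 and 9.4.2 and a little programming. No new blood draw, endpoint or sample size is needed. The downside of item 2 is that an earlier value stands in for Week 12, which pulls the estimate toward zero if the effect is still growing: −18.0 to −18.7 in the all-early case, and down to −17.6 if half of those children have no ET draw.
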